	To evaluate the safety of combining Deucravacitinib and Enstilar.
	To evaluate the subject quality of life when combining Deucravacitinib and Enstilar.
Study Design	30 adult patients with moderate to severe plaque psoriasis will be given Deucravacitinib 6mg QD for the first 8 weeks of the study.
	At week 8:
	Subjects who do not meet PASI 25 at week 8 will be discontinued from the study as non-responders.
	Subjects who achieve ≥PASI 75 at week 8 will remain enrolled and continue Deucravacitinib 6mg QD monotherapy through week 24.
	Subjects who achieved between PASI 25-74 response will receive 4 weeks of Enstilar (calcipotriene and betamethasone dipropionate) Foam, 0.005%/0.064% applied QD in addition to continuing Deucravacitinib 6mg QD.
	At week 12, (after 4 consecutive weeks of Enstilar), subjects in the PASI 25-74 group, will discontinue Enstilar QD and continue Deucravacitinib as monotherapy through week 24.
	Subjects will return at week 28 for safety follow evaluation.
Study Centers	Psoriasis Treatment Center of New Jersey

PTC09	30August202
Study Population	Adult male and female subjects with moderate to severe chronic plaque psoriasis
Main Inclusion Criteria	Subjects must meet the following criteria to be enrolled in this study: 1.Male or female adult ≥ 18 years of age; 2. Diagnosis of chronic plaque-type psoriasis 3. Moderate to severe plaque type psoriasis as defined at baseline by: • BSA affected by plaque-type psoriasis of 10% or greater • PGA score of 3 or greater • PASI ≥ 12. 4. Able and willing to give written informed consent prior to performance of any study-related procedures Must be in general good health (except for disease under study) as judged by the Investigator, based on medical history, physical examination, clinical laboratories, and urinalysis.

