Main Exclusion Criteria	Subjects who meet any of the following criteria will be excluded from participation in this study: 1. Other than psoriasis, any clinically significant (as determined by the investigator) cardiac, endocrinologic, pulmonary, neurologic, psychiatric, hepatic, renal, hematologic, immunologic disease, or other major disease that is uncontrolled. 2. Forms of psoriasis other than chronic plaque-type (e.g., Pustular erythrodermic and/or guttate psoriasis) or drug induced psoriasis 3. Use of oral systemic medications or PUVA phototherapy for the treatment of psoriasis within 4 weeks (includes, but not limited to, oral corticosteroids, methotrexate, acitretin and cyclosporine). 4. Prior use of biologics within the following periods: • Etanercept – 4 weeks • Adalimumab or certolizumab pegol – 8 weeks • IL-17 antagonists – 16 weeks • Ustekinumab or IL-23 pathway inhibitors – 24 weeks • Other biologics - 5 half-lives 5. Patient used topical therapies or UVB phototherapy to treat psoriasis within 2 weeks of the Baseline Visit (includes, but not limited to, topical corticosteroids, vitamin D analogs, or retinoids).

Study Drug Dosage and Administration	All subjects will receive Deucravacitinib 6mg daily at week 0 (baseline) through week 8. At week 8, patients who achieved between PASI 25-74 response will receive 4 weeks of Enstilar (calcipotriene and betamethasone dipropionate) Foam, 0.005%/0.064% once daily in addition to continuing Deucravacitinib 6mg daily. At week 12 (after 4 consecutive weeks of Enstilar therapy), Enstilar will be discontinued and patients will continue Deucravacitinib 6mg daily as monotherapy through week 24. Patients who achieve ≥PASI 75 at week 8 will remain enrolled on Deucravacitinib 6mg QD monotherapy through week 24.
Study Endpoints	Primary Endpoint: Proportion of subjects achieving PASI 75 at week 12 for patients in the Deucravacitinib + Enstilar combination arm. Secondary Endpoints: Proportion of subjects achieving PASI 25-74 at week 8. PASI, PGA, BSA, PGAxBSA and DLQI improvement at weeks 8, 12, 16, 20, 24. PASI 75 at weeks 16 and 24 Serious Adverse Events (SAE's)
Study Duration	28 weeks

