5.6.12 Early Discontinuation Procedures

Subjects will be prematurely discontinued from the study under the following conditions:

- 1. Subject does not reach PASI 25 or greater at week 8
- 2. Subject requests to withdraw from the study.
- 3. Subject is noncompliant with protocol schedule, restrictions, and/or requirements as deemed per investigator.
- 4. Subject experiences an adverse event that makes it difficult or intolerable for the subject to continue treatment, or increases risk to the subject, or interferes with the investigator's ability to clinically evaluate the progress of the subject's treatment.
- Subject begins an unapproved concomitant therapy for psoriasis or another medical condition that may increase risk to the subject if continuing study treatment.
- 6. Subject cannot be reached / lost to follow-up.
- 7. The study investigator suspends or terminates the study.
- 8. Other unanticipated reason.

Any subject who prematurely discontinues the study should complete the week 24 (End of Study) assessments and subjects should be encouraged return 4 weeks later for the safety follow up visit.

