8.2 Statistical Considerations

It is desired to enroll 30 patients. Since this is a pilot study with no formal hypothesis testing, statistical power/sample size is not formally presented in this protocol.

The study will analyze data based on the non-responder imputation (NRI) method. This will be performed for each arm of the study (PASI 75 responders at week 8 and PASI 25-74 responders at week 8. Subjects who do not complete week 12 assessments will be classified as non-responders

Analysis will be performed by the Investigator on proportion of subjects achieving Psoriasis Area Severity Index (PASI) 75 response at week 12

The investigator will also analyze PASI 25-74 at week 8, PASI, PGA, BSA, PGAxBSA and DLQI improvement at week 8, BSA, PGA and BSA x PGA and DLQI improvement at week 12. PASI, BSA, PGA, BSA x PGA and DLQI at weeks 16, 20 and 24. This analysis will be done separately for both cohorts (PASI 75 responders at week 8 and PASI25-74 responders at week 8) using summary statistics. The Investigator will also analyze SAE's by cohort.

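### Section 8.2 analyses by two week-8 responder cohorts only, so some treated subjects have no row in the SAE analysis and the week-8 PASI 25-74 endpoint has no usable denominator

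*Combined protocol and SAP*

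**What the plan says.** Section 8.2 gives the analysis rules, and the same two groups appear each time.

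- Non-responder imputation (NRI): "This will be performed for each arm of the study (PASI 75 responders at week 8 and PASI 25-74 responders at week 8".
- Summaries, after a list that runs from week 8 to week 24: "This analysis will be done separately for both cohorts (PASI 75 responders at week 8 and PASI25-74 responders at week 8) using summary statistics".
- Safety: "The Investigator will also analyze SAE's by cohort".

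The synopsis lists "Proportion of subjects achieving PASI 25-74 at week 8" as a secondary endpoint without saying of whom. It lists SAEs as an endpoint with no cohort restriction. Only the primary endpoint is tied to the combination arm.

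The design produces more than two groups. The synopsis states: "Subjects who do not meet PASI 25 at week 8 will be discontinued from the study as non-responders". Section 5.6.12 repeats this as a reason for early discontinuation, "Subject does not reach PASI 25 or greater at week 8", and adds reasons that can apply at any time, including withdrawal, loss to follow-up and "Subject experiences an adverse event that makes it difficult or intolerable for the subject to continue treatment".

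Neither section 8.2 nor any other section defines an all-enrolled, all-treated or safety population. The separate statistical plan in section 8.2.1 is optional and limited to exploratory work.

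**The concern.** A cohort defined by a week-8 result cannot contain a subject who has no week-8 result, and these two cohorts also exclude anyone below PASI 25. All of these subjects have taken deucravacitinib. If section 8.2 is followed to the letter, an SAE in such a subject is collected but appears in no planned analysis. That includes an SAE that caused the subject to leave.

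The week-8 endpoint has a related problem. The share of treated patients who become add-on candidates is a useful result from a pilot like this one. It needs a denominator fixed before week-8 response is known. Section 8.2 either conditions on the outcome being measured or leaves the denominator open.

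**Working it through.** The plan has no figure to reproduce. Section 8.2 sets a target of 30 subjects and disclaims any power calculation. The check is therefore of the text, followed by an illustration of size.

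**Step 1. Who is in a cohort.**

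| Subject's position at week 8 | Took deucravacitinib | Named in section 8.2 |
|---|---|---|
| PASI 75 or more | yes | yes |
| PASI 25-74 | yes | yes |
| Below PASI 25 (Synopsis; 5.1; 5.6; 5.6.12) | yes | no |
| Left before week 8 (5.6.12) | yes | no |

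**Step 2. The week-8 endpoint under each reading of the by-cohort sentence.**

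- If it governs the whole list before it, the proportion at PASI 25-74 is 100% in the PASI 25-74 cohort and 0% in the PASI 75 cohort, by definition. Week-8 PASI improvement is likewise confined by the cohort cut-offs. PGA, BSA and DLQI are not cut off directly.
- If it governs only the preceding item (weeks 16, 20 and 24), no population is stated for the week-8 endpoints.

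**Step 3. How much the denominator matters.** Let u be the number in neither cohort and a the number at PASI 25-74. The all-treated proportion is a/30, and the pooled-cohort proportion is a/(30 − u). The difference is [a/(30 − u)] × (u/30). Both u and the split are assumptions. About half of the placed subjects are put at PASI 25-74.

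| u | a | a/30 | a/(30 − u) | Difference (points) |
|---|---|---|---|---|
| 0 | 15 | 50.0% | 15/30 = 50.0% | 0 |
| 3 | 14 | 46.7% | 14/27 = 51.9% | 5.2 |
| 6 | 12 | 40.0% | 12/24 = 50.0% | 10.0 |
| 9 | 10 | 33.3% | 10/21 = 47.6% | 14.3 |

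The difference grows with the share at PASI 25-74. For u from 3 to 9, a share near 30% gives 3.0 to 8.6 points (8/27 − 8/30; 6/21 − 6/30). A share near 70% gives 7.0 to 21.4 points (19/27 − 19/30; 15/21 − 15/30).

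**Step 4. SAEs with no row.** Let p be the assumed chance that an unplaced subject has at least one SAE, independent between subjects. The chance that at least one unplaced subject has an SAE is 1 − (1 − p)^u.

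| u | p = 2% | p = 5% |
|---|---|---|
| 3 | 5.9% | 14.3% |
| 6 | 11.4% | 26.5% |
| 9 | 16.6% | 37.0% |

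As an example of the effect on a rate, take u = 6, one subject with an SAE among the 6 and one among the other 24. The two cohorts show 1/24 = 4.2%; all treated subjects show 2/30 = 6.7%.

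**The case against.** The strongest reply is that these subjects are not ignored. Section 8.2 has a free-standing sentence that treats anyone without week-12 assessments as a non-responder, and it carries no explicit cohort limit. The synopsis also gives that label to subjects below PASI 25. A reader might infer from the two-cohort wording that these subjects have no classification anywhere. The documents do not support that, because the week-12 sentence may well cover them. It reaches only week 12, however, and settles neither the week-8 denominator nor the SAE row.

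A second reply is that the 100% and 0% result is unlikely in practice. The wording of section 8.2 is loose, the synopsis ties only the primary endpoint to the combination arm, and all subjects are treated alike up to week 8. This stands in part. All subjects were probably intended, and the circular reading, though the most direct, is not the only one. The other reading still leaves the denominator unstated.

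A third reply concerns safety. SAEs are collected from consent on everyone and reported to the drug supplier, and cases are reconciled every 3 months and before database lock. Non-serious events go to the supplier in aggregate through study reports (all in section 6). The safety objective is worded for the combination, which the unplaced subjects never received. A reader might infer that safety data would be lost; that would be wrong. The gap is in the planned analysis only. The wording of the objective does not close it, since section 8.2 already analyses SAEs in the monotherapy cohort and the synopsis endpoint is unrestricted.

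Finally, this is a small descriptive pilot, and the missing share could be rebuilt from cohort sizes if they are shown. That limits the harm. But descriptive proportions are the main output of such a study, and section 8.2 does not ask for this one.

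**Conclusion.** The point holds. Section 8.2 gives a positive instruction to analyse by two cohorts, and that instruction leaves out SAEs in treated subjects who are in neither. It also makes the week-8 PASI 25-74 endpoint either fixed by definition or without a stated denominator.

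The size cannot be derived from the documents, which give no response, dropout or SAE rates. Under the central assumptions (3 to 9 of 30 unplaced, about half of the rest at PASI 25-74) the week-8 proportion moves by about 5 to 14 percentage points according to the denominator. It does not move if nobody is unplaced. The chance that at least one unplaced subject has an SAE is 6% (3 subjects, 2% risk) to 37% (9 subjects, 5% risk).

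A reader might extend this to the primary endpoint. The documents do not support that: the primary endpoint is restricted by design to the combination arm, with its own week-12 rule. Nor is any comparison of groups distorted, because section 8.2 plans no formal hypothesis test.

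**What to change.** In section 8.2, define an all-treated set: every subject who took at least one dose of deucravacitinib (planned 30). On that set, report:

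- week-8 PASI response in four rows (below 25, 25 to below 75, 75 or more, missing), with the 25 to below 75 row over all treated as the secondary endpoint;
- week-8 improvement in PASI, BSA, PGA, the product of PGA and BSA, and DLQI, with the number missing;
- SAEs overall and by cohort, with a line for subjects in neither cohort.

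Keep the two cohorts for visits after week 8, and leave the primary endpoint and its NRI rule as they are.

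The cost is a few sentences and one extra table column. No new data are needed: the schedule in section 8.3 already has PASI, BSA, PGA, DLQI and adverse events at week 8, and section 6 already collects SAEs from consent. Week-8 results may look less favourable than in the two cohorts alone, by an amount that depends on how many subjects are below PASI 25.

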5. INVESTIGATIONAL PLAN

5.1 Overall Study Design and Plan

30 subjects affected with plaque psoriasis with body surface area greater than or equal to 10%, and physician's global assessment greater than or equal to 3 and PASI greater than or equal to 12 will receive deucravacitinib 6 mg once daily for 8 weeks. Subjects who do not achieve at least a PASI 25 at week 8 will be discontinued from treatment and study procedures.

At week 8, subjects who have achieved between a PASI 25-74 will receive Enstilar (calcipotriene and betamethasone dipropionate) Foam, 0.005%/0.064% once daily for 4 weeks in addition to continuing deucravacitinib 6mg daily. These subjects will then discontinue Enstilar at week 12 and remain on deucravacitinib monotherapy through week 24.

Subjects who achieve ≥PASI 75 at week 8 will remain enrolled in the study and continue deucravacitinib QD through week 24. These subjects will not receive Enstilar add-on therapy.

All subjects will be asked to return for a safety follow up visit 4 weeks after the last dose of deucravacitinib.

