5.5.2.3 Deucravacitinib Dosage Adjustments

If an SAE or an adverse event that is thought to be related to deucravacitinib and is not alleviated by symptomatic intervention, deucravacitinib will be discontinued. Subjects who permanently discontinue deucravacitinib therapy under this protocol should receive standard care of psoriasis treatment as prescribed by their physician.

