5.5.3.4 Enstilar Dosage Adjustments

If an SAE or an adverse event that is thought to be related to Enstilar and is not alleviated by symptomatic intervention, Enstilar will be discontinued.

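### The only SAE analysis specified is by week-8 response cohort: as written, it omits treated subjects in neither cohort and does not isolate the combination period

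*Combined protocol and SAP*

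**What the plan says.** The Protocol Synopsis gives as a secondary objective: "To evaluate the safety of combining Deucravacitinib and Enstilar". It lists SAEs as a secondary endpoint, without a population, period or method.

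Section 8.2 supplies the only analysis: "The Investigator will also analyze SAE's by cohort". The sentence just before it, on the efficacy and DLQI summaries, reads: "This analysis will be done separately for both cohorts (PASI 75 responders at week 8 and PASI25-74 responders at week 8) using summary statistics". Section 8.2 states no all-treated safety set and no rule that ties an SAE to the treatment in use at onset.

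The treatment paths are as follows.

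- All 30 planned subjects start deucravacitinib at baseline.
- Section 5.1, on low response: "Subjects who do not achieve at least a PASI 25 at week 8 will be discontinued from treatment and study procedures".
- Section 5.1, on the PASI 25-74 group after four weeks of Enstilar: "These subjects will then discontinue Enstilar at week 12 and remain on deucravacitinib monotherapy through week 24".
- Section 5.5.2.3 covers an SAE, or an adverse event thought to be drug-related. Where it "is not alleviated by symptomatic intervention, deucravacitinib will be discontinued". Section 5.6.12 separately lists an intolerable adverse event as a reason to leave the study.
- Section 5.5.3.4 has a parallel rule for an event "thought to be related to Enstilar and is not alleviated by symptomatic intervention, Enstilar will be discontinued".

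Section 8.2.1 allows further exploratory analysis at the sponsor-investigator's discretion and commits to none.

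**The concern.** Membership of either cohort depends on a PASI response measured at week 8, eight weeks after every subject has started deucravacitinib. Grouping SAEs this way raises two separate problems.

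**Incomplete population.** A subject who leaves before week 8 has no week-8 PASI, and a subject below PASI 25 at week 8 meets neither definition. The first omission is linked to the outcome being counted: an SAE that ends participation early also removes the subject from the table. The deucravacitinib SAE summary may then look too favourable.

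**Combination not isolated.** The PASI 25-74 cohort takes deucravacitinib alone for weeks 0-8, the combination for weeks 8-12, and deucravacitinib alone again for weeks 12-24. A count over the whole course pools all three. Raw counts may credit monotherapy events to the combination. A rate, or a comparison with the PASI 75 cohort, may dilute an excess confined to the four combination weeks.

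**Working it through.** The plan states no SAE rate, power or sample-size figure, so there is nothing of its own to reproduce. The check compares the cohort definitions with the treatment paths and then works out exposure.

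**Part 1: who has a place in the by-cohort table**

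| Path after the first deucravacitinib dose | Cohort in 8.2 |
|---|---|
| PASI 75 or better at week 8 | PASI 75 cohort |
| PASI 25-74 at week 8 | PASI 25-74 cohort |
| Below PASI 25 at week 8 (5.1, 5.6.12) | none |
| Left the study before week 8 (5.6.12) | none |

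Three provisions might seem to close the gap, and none does.

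- Section 5.6.12 asks early leavers to complete the week 24 assessments, which include PASI (Schedule of Events). That is not a week-8 PASI, and no rule maps it to a cohort.
- Non-responder imputation in 8.2 assigns a response status; non-responders are not one of the two cohorts.
- Section 6 collects these subjects' SAEs and reports them to the manufacturer. It specifies no study analysis.

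The documents do not say how many subjects will be in neither cohort. Per subject with an SAE: 1/30 = 3.3% of the planned treated number, entered as 0.

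For a range, assume that m subjects are in neither cohort and that each has SAE risk r. Omitted exposure is at most 8m person-weeks of deucravacitinib, and the chance of at least one omitted SAE is 1 − (1 − r)^m.

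- m = 3, 6, 9: up to 24, 48, 72 person-weeks.
- m = 3, r = 1%: 1 − 0.99³ = 3.0%.
- m = 9, r = 5%: 1 − 0.95⁹ = 37.0%.

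Both m and r are assumptions.

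**Part 2: share of the PASI 25-74 cohort's course spent on the combination**

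Inputs from 5.1: dosing for 24 weeks = 168 days; Enstilar in weeks 8-12 = 28 days; the other 20 weeks = 140 days on deucravacitinib alone. Share on the combination: 28/168 = 16.7%.

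Assume that the SAE rate on the combination is k times a constant monotherapy rate, with full completion and no carry-over after Enstilar stops. The cohort's rate relative to monotherapy is then as follows.

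| Setting | Formula | k = 2 | k = 3 | k = 5 |
|---|---|---|---|---|
| 28 days of Enstilar, 168 days counted | (28k + 140)/168 = (k + 5)/6 | 1.17 | 1.33 | 1.67 |
| Enstilar stopped after 14 days (assumed) | (14k + 154)/168 = (k + 11)/12 | 1.08 | 1.17 | 1.33 |
| Counted to 30 days after last dose (198 days) | (28k + 170)/198 | 1.14 | 1.28 | 1.57 |

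Raw counts mislead in the other direction. Under the first setting, the share of the cohort's expected SAEs that arise on monotherapy is 140/(28k + 140) = 5/(k + 5): 83.3% for k = 1, 62.5% for k = 3 and 50% for k = 5. The k values show a range; they are not estimates.

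**The case against.** The strongest reply is that the SAE sentence says neither both nor only. The two-cohort definition belongs to the preceding sentence, on efficacy and DLQI, and a third row for unclassified subjects would be compatible with the text. That stands as a limit: the first part holds for the plan as written, and an investigator could add such a row unprompted. But 8.2 names no other cohort and does not ask for one.

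Subjects in neither cohort never receive Enstilar, so their events do not bear on the safety of the combination. This is right for the stated objective. It does not excuse leaving them out of the SAE endpoint, which the synopsis lists without restriction.

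Section 5.5.2.3 concerns stopping the drug, not leaving the study, so a subject who stopped early but attended week 8 could still be classified. That is correct, but 5.6.12 makes an adverse event that prevents continued treatment a ground for leaving the study.

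No data are lost: under Section 6, SAEs are collected from consent to 30 days after dosing, a physician assesses causality, and cases are reconciled every three months. This limits the harm. Causality assessment helps with single events, but it gives no count or number at risk by period.

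The multipliers rest on assumptions, and because collection begins at consent, neither 168 nor 198 days is the full window. Both points are accepted. The 28-of-168 share is the plan's own schedule and needs no assumption about event rates. Finally, if SAEs are few, a listing may serve as well as a table, and the fix allows for that.

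**Conclusion.** The concern holds in both parts, for 8.2 as written.

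1. Treated subjects who are below PASI 25 at week 8, or gone before it, have no place in the one SAE analysis specified. Their number is unknown. Each one with an SAE is 3.3% of 30 planned treated subjects, shown as zero.
2. The analysis does not isolate the combination. Only 16.7% of planned dosing days in the PASI 25-74 cohort are on it, and an assumed threefold rate in that period would appear as 1.33 times the monotherapy rate over 24 weeks.

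The consequence is an incomplete and hard-to-interpret descriptive safety summary in a 30-subject pilot. No test, power or error rate is affected. It should be fixed, because combination safety is a stated secondary objective and the repair is cheap.

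**What to change.** In 8.2, state the following.

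- SAEs are analysed in all subjects who took at least one dose of deucravacitinib, with a row for those in neither cohort.
- Each SAE is tabulated, or listed if there are few, by the actual treatment in use at onset rather than by calendar week: before Enstilar; on deucravacitinib plus Enstilar, from first to last recorded Enstilar use; after Enstilar, with days since last recorded use; or deucravacitinib alone throughout.
- The number of subjects at risk is shown for each period.
- The by-cohort table is kept as secondary.

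The cost is two or three sentences and one extra table or listing. Enstilar use is already captured in the dispensing records (5.5.3.3) and the 28-day diary (Appendix A). The split needs SAE onset dates, which the documents imply but do not state; if they are not recorded, one field must be added. No dose, visit or clinical rule changes.

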3.2 Rationale for Treating Plaque Psoriasis with Deucravacitinib + Enstilar

Deucravacitinib is an investigational TYK2 inhibitor that has been tested for the treatment of moderate-to-severe psoriasis. Combination regimens that utilize a systemic agent with light therapy and/or a topical agent are becoming the standard of care in the United States³ and Europe⁴, confirming the observation of Lebwohl et al⁵ in 2004, that the use of two or more therapies to treat patients with moderate to severe psoriasis seems to be the rule rather than the exception. Topical steroids play an in important role in the long-term management of psoriasis and data from the COBRA trial suggests that super potent topical corticosteroids are appropriate and well tolerated for use when added to existing therapeutic regimens i.e. phototherapy, systemic and biologic therapy.⁶ In a similarly designed clinical trial using apremilast with Enstilar add- on therapy it was shown that most week-8 partial apremilast responders achieved PASI 75 at week 12 with combination C/BD topical therapy, and maintained PASI 75 through week 16 with apremilast monotherapy.⁷ This study is being conducted to determine if adding topical Enstilar to deucravacitinib therapy can help patients who received a partial response at week 8 reach PASI 75 by week 12.

4.STUDY OBJECTIVES

The primary objective of this study is to explore the effectiveness of combining deucravacitinib and Enstilar. Secondary objectives will explore the safety and impact on quality of life for subjects receiving deucravacitinib in combination with Enstilar.

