It is the Sponsor-Investigator's responsibility to report events to their Local HA. In addition, suspected serious adverse reactions (whether expected or unexpected) shall be reported by BMS to the relevant competent health authorities in all concerned countries according to local regulations (either as expedited and/or in aggregate reports).

In accordance with local regulations, BMS will notify Sponsor-Investigator of all reported SAEs that are suspected (related to the investigational product) and unexpected (ie, not previously described in the IB). An event meeting these criteria is termed a **Suspected, Unexpected Serious Adverse Reaction (SUSAR)**. Sponsor-Investigator notification of these events will be in the form of either a SUSAR Report or a Semi-Annual SUSAR Report. Sponsor-Investigator (or delegate) will receive these reports through the FastTrack portal.

Other important findings which may be reported by BMS as an Expedited Safety Report (ESR) include: increased frequency of a clinically significant expected SAE, an SAE considered associated with study procedures that could modify the conduct of the study, lack of efficacy that poses significant hazard to study subjects, clinically significant safety finding from a nonclinical (eg, animal) study, important safety recommendations from a study data monitoring committee, or Sponsor-Investigator or BMS decision to end or temporarily halt a clinical study for safety reasons.

Upon receiving an ESR from BMS, the Sponsor-Investigator **must review and retain the ESR with the IB**. Where required by local regulations or when there is a central IRB/IEC for the study, the Sponsor-Investigator will submit the ESR to the appropriate IRB/IEC. The investigator and IRB/IEC will determine if the informed consent requires revision. The investigator should also comply with the IRB/IEC procedures for reporting any other safety information.

NON-SERIOUS ADVERSE EVENT COLLECTION AND REPORTING

The collection of non-serious AE information should begin following the subject's written consent to participate in the study. All non-serious adverse events (not only those deemed to be treatment-related) should be collected continuously during the treatment period and for a minimum of 30 days following the last dose of study treatment.

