Non-serious AEs should be followed to resolution or stabilization, or reported as SAEs if they become serious. Follow-up is also required for non-serious AEs that cause interruption or discontinuation of study drug and for those present at the end of study treatment as appropriate.

Non-serious Adverse Events (AE) are to be provided to BMS in aggregate via interim or final study reports as specified in the agreement or, if a regulatory requirement [eg, IND US trial] as part of an annual reporting requirement.

PREGNANCY

If, following initiation of the investigational product, it is subsequently discovered that a study participant is pregnant or may have been pregnant at the time of investigational product exposure, including during at least 5 half-lives after product administration, the investigational product will be permanently discontinued in an appropriate manner (eg, dose tapering if necessary for participant).

The Sponsor-Investigator must immediately notify [contact] of this event and complete one of the following forms within 24 hours of awareness of the event via either the CIOMS, MedWatch or appropriate Pregnancy Surveillance Form in accordance with **SAE reporting procedures**.

Protocol-required procedures for study discontinuation and follow-up must be performed on the participant.

Follow-up information regarding the course of the pregnancy, including perinatal and neonatal outcome and, where applicable, offspring information must be reported on the CIOMS, MedWatch, BMS Pregnancy Surveillance Form, or approved site SAE form. A BMS Pregnancy Surveillance Form may be provided upon request.

Any pregnancy that occurs in a female partner of a male study participant should be reported to BMS. Information on this pregnancy will be collected on the Pregnancy Surveillance Form. In order for Sponsor-Investigator or designee to collect any pregnancy surveillance information from the female partner, the female partner must sign an informed consent form for disclosure of this information.

LABORATORY TEST ABNORMALITIES

All laboratory test results captured as part of the study should be recorded following institutional procedures. Test results that constitute SAEs should be documented and reported to BMS as such.

The following laboratory abnormalities should be documented and reported appropriately:

- any laboratory test result that is clinically significant or meets the definition of an SAE

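### Safety of the combination is a secondary objective, but the only safety analysis planned is SAEs by week-8 response cohort, with no summary of non-serious AEs for the subjects or the period on both products

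*Combined protocol and SAP*

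**What the plan says.** The synopsis gives as a secondary objective "To evaluate the safety of combining Deucravacitinib and Enstilar". Section 4 puts it in terms of people: "Secondary objectives will explore the safety and impact on quality of life for subjects receiving deucravacitinib in combination with Enstilar". The synopsis list of endpoints names SAEs and no other safety measure. Section 8.2 has one sentence on safety: "The Investigator will also analyze SAE's by cohort". Its two cohorts are defined by PASI response at week 8.

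The two products overlap only in the PASI 25-74 cohort, from week 8 to week 12. Section 5.1 then says: "These subjects will then discontinue Enstilar at week 12 and remain on deucravacitinib monotherapy through week 24".

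On non-serious events, section 6 states: "All non-serious adverse events (not only those deemed to be treatment-related) should be collected continuously during the treatment period". It also says that they "are to be provided to BMS in aggregate via interim or final study reports as specified in the agreement". It mentions no cohort or treatment period. Section 8.2.1 permits further exploratory analysis under a separate plan, at the sponsor-investigator's discretion.

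**The concern.** The objective concerns what happens when a topical product is added to an oral one for 4 weeks. Tolerability problems with such an add-on would be expected to show mostly as non-serious AEs, and these are outside the planned analysis. SAEs, the one planned measure, will be few in a cohort drawn from 30 subjects. The count by cohort also pools the weeks on both products with a much longer time on deucravacitinib alone.

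At stake is whether the report answers its own safety objective. The study is open-label, and the sponsor is also the principal investigator, who performs the analysis (section 8.2) and monitors the records (section 8.1). Naming the safety summary beforehand avoids having it chosen after the events are known.

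**Working it through.** The plan has no figure to reproduce: section 8.2 describes a pilot without hypothesis tests and gives no power calculation.

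**Inputs from the documents.** Total enrollment is 30 (section 8.2). Deucravacitinib is given for 24 weeks, with Enstilar in weeks 8 to 12, and the safety visit is at week 28 (synopsis, sections 5.1 and 8.3).

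**Assumed inputs.** The documents do not give the size of the PASI 25-74 cohort; 10 to 20 is used. They give no SAE rate; 2 to 10 per 100 patient-years is used. Follow-up is taken as complete and events as Poisson.

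**Share of combined use.** 4/24 = 16.7% of dosing weeks. The other 24 - 4 = 20 weeks are deucravacitinib alone.

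**What zero SAEs would exclude.** The exact one-sided 95% upper limit with 0 events in n subjects is 1 - 0.05^(1/n). It needs no assumed event rate and applies to the risk over whichever period is counted.

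- n = 10: 25.9%
- n = 15: 18.1%
- n = 20: 13.9%
- n = 30, if every subject were in the cohort: 9.5%

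**Chance of no SAE.** Patient-years = n × weeks/52; expected SAEs = patient-years × rate; P(none) = exp(-expected).

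| Period counted | n | Patient-years | Rate per patient-year | Expected SAEs | P(none) |
|---|---|---|---|---|---|
| Whole cohort follow-up, 28 weeks | 10 | 5.4 | 0.02 | 0.11 | 90% |
| Whole cohort follow-up, 28 weeks | 20 | 10.8 | 0.10 | 1.08 | 34% |
| Weeks 8 to 12 only | 10 | 0.77 | 0.02 | 0.015 | 98% |
| Weeks 8 to 12 only | 20 | 1.54 | 0.10 | 0.154 | 86% |

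The first two rows correspond to the analysis planned in section 8.2. The last two correspond to a window that the plan does not define. As a cross-check on the cohort rows, an assumed SAE risk per subject of 1% to 5% gives a chance of at least one SAE of 1 - 0.99^10 = 9.6% to 1 - 0.95^20 = 64.2%, close to the 10% to 66% implied by the table.

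**What AEs of any grade could add.** An AE with an assumed 10% risk over the 4 weeks would be seen at least once with probability 1 - 0.9^n: 65% for n = 10 and 88% for n = 20. At an assumed 1 to 4 AEs per patient-year, 0.77 × 1 = 0.8 to 1.54 × 4 = 6.2 events are expected in the window. That is enough to describe events, but too few to compare rates.

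**The case against.** The strongest reply is that this is a 30-subject descriptive pilot whose safety objective is exploratory. Non-serious AEs are collected throughout, and the table can be made at reporting. Under section 4 the objective concerns the subjects who receive the combination, and section 8.2 already reports that cohort separately. The agreement with BMS, which is not among the documents, may specify a split of the aggregate report.

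Much of this stands. It sets the severity, and it rules out three stronger readings that a reader might infer:

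- *Non-serious AEs go uncollected or unreported.* Section 6 requires both collection and aggregate supply to BMS. The gap is only that the protocol states no split.
- *The planned SAE analysis will almost surely be empty.* The 98% to 86% applies to weeks 8 to 12 alone. The planned count covers the cohort's full follow-up, where the chance of none runs from about 90% down to 34%.
- *The objective can only mean weeks 8 to 12.* The synopsis wording allows that reading, while section 4 points to the subjects. The documents do not settle it.

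The reply does not close the gap on either reading. If the objective means the subjects, the cohort is right but SAEs are the only planned measure. If it means the period of combined use, no onset window is planned either. Section 8.2.1 is optional and commits to nothing.

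**Conclusion.** The concern holds as a gap between a stated objective and the analysis planned for it. SAEs by cohort carry little information at this size: with 10 to 20 subjects, zero SAEs leaves a risk of up to about 26% to 14% compatible with the data. That result rests only on the assumed cohort size. The probabilities of seeing no SAE also rest on an assumed event rate and complete follow-up; dropout would lower exposure and make no SAE more likely.

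The primary endpoint is unaffected, AE collection is in place, and nothing in the documents suggests that subjects are less well protected. An all-AE table would describe tolerability; it would not establish that the combination is safe. This is a low-severity improvement, worth making because it is cheap.

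**What to change.** In section 8.2, replace the SAE sentence with:

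> All AEs (serious and non-serious) from first dose will be summarized descriptively for all treated subjects and by cohort, with subjects below PASI 25 or leaving before week 8 shown as a separate group; events between consent and first dose will be listed. For the PASI 25-74 cohort, AEs will also be summarized by onset: before the first Enstilar application, from first to last Enstilar application, and after the last application to the end of AE collection, with events, subjects with an event and exposure time for each, and the number who stopped Enstilar for an AE. Laboratory abnormalities first seen at week 16 will be flagged as of uncertain onset. No hypothesis test is planned.

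The separate group is needed because those subjects belong to neither cohort in section 8.2. Actual application dates, which the Appendix A diary records, avoid nominal weeks that overlap at the visits. The laboratory flag is needed because section 5.6.5 schedules no tests between screening and week 16.

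The cost is one descriptive table with small counts that cannot show a rate difference. AEs are already recorded at the week 8 and week 12 visits (section 8.3). Section 5.5.3.4 provides that after "an adverse event that is thought to be related to Enstilar and is not alleviated by symptomatic intervention, Enstilar will be discontinued", but it does not show that the reason is recorded, so that field must be added if it is missing. No new visits, procedures or subjects are needed.
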